### **Power**

Our previous studies have shown that CNV status accounts for up to 38% of the variation in the range of phenotypic outcome measures we have studied (i.e., psychiatric conditions, other neurodevelopmental problems, including motor coordination, cognitive function, social and other behaviour, and sleep disturbance). However, we have a power of 80% to detect differences in trajectory between 500 children with pathogenic CNV and 150 siblings at a significance level of 0.01 (corrected for 5 trajectories) for CNV effects accounting for as little as 2% of variance. Our work indicates that the different CNV genotypes account for up to 22% of the variance of these individual phenotypes. For a sample of 500 affected individuals, we have power of 80% to detect differences in trajectory between 13 different CNVs at a significance level of 0.01 (corrected for 5 trajectories) for CNV effects accounting for as little as 5% of variance. We have 80% power to detect an effect of PRS accounting for 3% of variance in trajectory in 500 participants at a significance level of 0.0025 (corrected for 5 trajectories and 4 PRS). Such effects are reasonable, given that 7% of the variance in schizophrenia liability is accounted for by PRS.

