Study Endpoints	Data on child neurodevelopment and psychopathology and factors that influence this
Sample Size	
Workstream 1: n=3,402 Workstream 2: n=520

Summary of eligibility criteria	
Recruited for IMAGINE-1:
 
i) Participant has an intellectual disability; ii) Participant has had a diagnostic microarray by an accredited Regional Genetic Centre, or has had next-generation sequencing; iii) Participant has at least one Copy Number Variant or Single Nucleotide Variant reported as pathogenic; iv) There is a legal guardian available to consent and provide detailed medical and behavioural history.
 
Self-referrals for IMAGINE-2:
 
i) Participant has an intellectual disability; ii) Participant has had a diagnostic microarray by an accredited Regional Genetic Centre, or has had next-generation sequencing; iii) Participant has at least one Copy Number Variant or Single Nucleotide Variant reported as

	pathogenic; iv) There is a legal guardian available to consent and provide detailed medical and behavioural history; v) aged 4 to 26 at recruitment.
Procedures: Screening & enrolment	Conducted as part of IMAGINE-1 (NHS REC: 13/LO/1069)

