## 4.3 Study Design

We are conducting a 5-year longitudinal study of the cohort with annual online phenotyping of all participants and linking to administrative records (Workstream 1), supplemented by intensive face-to-face assessments of 520 young people with highly pathogenic CNV that were intensively studied in our first phase (Workstream 2). Two research centres are involved: University College London's Great Ormond Street Institute of Child Health and Cardiff University's Neuroscience and Mental Health Research Unit.

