## Population

Our genotype-first study IMAGINE-1 recruited 3,402 children from UK NHS Regional Genetics Clinics, whose intellectual disability (ID) is associated with either a pathogenic Copy Number Variant (CNV- 75.9%) or Single Nucleotide Variant (SNV- 23.6%) or both (0.5%). 84% of consented families provided standardized assessments of their child's mental health, functional adaptation, medical and educational history, and family/social environment, by completing online questionnaires. We have data on 4,054 genetic variants, logged for 3,398 individuals, representing 3,117 CNVs (1,534 in recognised syndromes, 1,583 unique) and 944 SNVs in 278 different genes. 57% of IMAGINE-1 participants had one or more psychiatric diagnoses: Autism Spectrum Disorders (38%); ADHD (24%); anxiety disorders (12%); challenging behaviour (13%). 31% had a history of seizures, of whom 57% take anticonvulsant medication.

A subset of this group comprised 520 individuals with a specific range of CNVs and their siblings. These comprised children with 16 CNVs across 9 loci. All families in this subset were visited at home for individual face-to-face assessments and agreed to be re-contacted for future studies. We aim to make contact at least 500 participant families. With permission (and with due regard to Covid restrictions) they will be reassessed during a face-to-face visit, with a focus on the affected child as well as the children's unaffected (control) siblings who had been recruited as part of IMAGINE-1.

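### The three 80% power statements for Workstream 2 allow for no loss to follow-up, and the polygenic-score and between-CNV claims have little or no room for any

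*Protocol*

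**What the plan says.** Protocol section 6.1, Power, makes three claims of 80% power for Workstream 2.

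- **Carriers against siblings:** "we have a power of 80% to detect differences in trajectory between 500 children with pathogenic CNV and 150 siblings". The effect is 2% of variance and α is 0.01, which adjusts for five trajectories.
- **Between CNVs:** "For a sample of 500 affected individuals, we have power of 80% to detect differences in trajectory between 13 different CNVs". Here α is again 0.01 and the effect is 5% of variance.
- **PRS:** 3% of variance in 500 participants at 0.0025, correcting for 5 trajectories and 4 scores.

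The numbers behind these claims appear elsewhere in the protocol.

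- Synopsis (section 3): "Workstream 1: n=3,402 Workstream 2: n=520", with no split into carriers and siblings.
- Section 4.3, Study Design: "supplemented by intensive face-to-face assessments of 520 young people with highly pathogenic CNV", that is, carriers only.
- Population: "A subset of this group comprised 520 individuals with a specific range of CNVs and their siblings", which can be read with or without the siblings inside the 520. The count of CNVs given there is 16, across 9 loci.
- Population, on follow-up: "We aim to make contact at least 500 participant families". No number to be reassessed or analysed is given.
- Section 4.4, Workstream 2 criteria: 150 is the number of control siblings who took part in IMAGINE-1.
- Section 5.2: families choose which parts of the study to join, and the sibling's consent to the face-to-face visit is optional.
- Section 5.5: Workstream 2 has one follow-up assessment, about five years after the first visit.
- Section 6.1, Workstream 2 analysis, item iii: 13 CNVs are compared.

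**The concern.** The power text treats 500 and 150 as analysed numbers. The first matches a contact target and the second is the whole baseline sibling group. Between contact and analysis lie consent to the face-to-face part, separate consent for the sibling, the visit itself and withdrawal. None of these is allowed for.

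This matters because the outcome is a trajectory. Under item i of the Workstream 2 analysis, the measures tested come from individual random effects for trajectory in a mixed model. With one follow-up visit, a child who misses it contributes nothing on within-person change. If loss eats into the 500 and the 150, the effects described as detectable at 80% power are not detectable at that power, and a null PRS or between-CNV result would be read as stronger evidence than it is.

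The count of CNVs affects the same claim. More groups at the same sample size cost power, and the protocol gives both 13 and 16.

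**Working it through.** **Method.** F test in regression or analysis of variance. With R² the variance explained, f² = R²/(1 − R²), noncentrality λ = N·f², numerator degrees of freedom u and denominator N − u − 1. Power is the probability that a noncentral F exceeds the critical value at the stated α. Sidedness is not stated, so a non-directional test is assumed.

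**Inputs (section 6.1, Power).**
- Siblings: N = 500 + 150 = 650, u = 1, α = 0.05/5 = 0.01, R² = 2%.
- Between CNVs: N = 500, u = 12 (13 groups) or 15 (16 groups, Population), α = 0.01, R² = 5%.
- PRS: N = 500, u = 1, α = 0.05/20 = 0.0025, R² = 3%.

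**Step 1: reproduce the plan.**
- Siblings: λ = 650 × 0.02/0.98 = 13.27; power 85.5%.
- 13 CNVs: λ = 500 × 0.05/0.95 = 26.32; power 84.8%.
- PRS: λ = 500 × 0.03/0.97 = 15.46; power 81.4%.

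All three are at or above 80%. The smallest R² detectable at exactly 80% power is 1.77%, 4.62% and 2.93%, which round to the stated 2%, 5% and 3%. With 16 CNVs, power is 80.2%.

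**Step 2: how much loss each claim can bear.**

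| Claim | N needed for 80% | N assumed | Slack |
|---|---|---|---|
| Siblings, 2% | 576 | 650 | 11.4% |
| 13 CNVs, 5% | 461 | 500 | 7.8% |
| 16 CNVs, 5% | 499 | 500 | 0.2% |
| PRS, 3% | 488 | 500 | 2.4% |

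**Step 3: what 500 and 150 imply.** If the 520 are all carriers, 500 analysed is 500/520 = 96% retention over about five years. The siblings need 150/150 = 100%.

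**Step 4: power over an assumed retention range.** The protocol gives no Workstream 2 retention figure, so these rates are assumptions, applied to the 500 and 150.

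| Retention (carriers + siblings) | Siblings | 13 CNVs | 16 CNVs | PRS |
|---|---|---|---|---|
| 100% (500 + 150) | 85.5% | 84.8% | 80.2% | 81.4% |
| 90% (450 + 135) | 80.8% | 78.5% | 73.1% | 75.4% |
| 85% (425 + 128) | 78.0% | 74.7% | 69.0% | 72.0% |
| 80% (400 + 120) | 74.9% | 70.5% | 64.5% | 68.2% |

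**Step 5: variance detectable at 80% power.** At 90% retention: 2.0% (siblings), 5.1% or 5.5% (13 or 16 CNVs), 3.2% (PRS). At 80%: 2.2%, 5.7% or 6.2%, 3.6%.

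**Step 6: sensitivity to the starting count.** If the 520 are all carriers and retention is applied to 520 and 150, then 90% leaves 468 + 135. Power is then 82.2% (siblings), 80.9% or 75.8% (13 or 16 CNVs) and 77.7% (PRS). On that base, the retention of carriers needed for 80% power is 461/520 = 88.7% (13 CNVs), 488/520 = 93.8% (PRS) and 499/520 = 96.0% (16 CNVs).

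**The case against.** The strongest reply is that nothing is miscalculated. At 500 and 150 the claims are met, two of them with room to spare, and if all 520 carriers and 150 siblings were analysed power would be 86.7%, 86.8% (13 CNVs) and 83.4%. That stands: the fault is in the inputs, not the arithmetic. It is also true that every family in the subset agreed to be recontacted, that mixed models in an accelerated longitudinal design can use children with one visit, and that the sibling contrast withstands about 11% loss. But agreeing to recontact is not completing a visit, and single-visit children add little on individual change.

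A reader might go further in three ways that the documents do not support.

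- **Only 370 carriers exist (520 − 150).** This follows from one reading of the Population sentence. Section 4.3 describes the 520 as carriers, and the same Population paragraph aims at 500 or more families, each entering through an affected child; 370 carriers cannot come from 500 families. It is the least consistent reading, and the most that can be said is that the wording is unclear.
- **Retention will be 84%.** That figure in the Population section is the share of consented IMAGINE-1 families who completed online questionnaires. It is neither a retention rate nor a Workstream 2 figure.
- **Workstream 1 is overstated in the same way.** The power text makes no claim for Workstream 1, and section 6.1 already puts the follow-up pool with baseline measures at about 3,000.

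**Conclusion.** The concern holds in a limited form. The power statements are correct for 500 carriers and 150 siblings analysed, but the protocol does not support those as analysed numbers and makes no allowance for loss. The PRS claim falls below 80% once more than 12 of the 500 carriers are lost. The between-CNV claim does so after 39 with 13 groups, or after one with 16. The sibling contrast is the least exposed: it holds at 90% retention and is at 78.0% at 85%.

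The size is moderate. At 80 to 90% retention of 500 and 150, PRS power is about 68 to 75% and between-CNV power about 71 to 79% (13 groups) or 65 to 73% (16 groups). Detectable variance rises by fractions of a percentage point to a little over one point. These figures assume a non-directional F test, R² held at the stated values, equal proportional loss in carriers and siblings, and children without follow-up contributing nothing.

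Two counts remain unresolved: whether the 520 includes siblings, and 13 against 16 CNVs. The documents do not show that 16 is the right number of groups; 13 may be an analysed subset. It would be wrong to conclude that the study cannot reach 80% power. With all 520 as carriers and high retention, it can.

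**What to change.** Four edits to the protocol:

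1. State the carriers and siblings seen face to face in IMAGINE-1 as two separate numbers, and use them consistently in the synopsis, section 4.3, the Population section and section 4.4.
2. Reconcile 13 with 16 CNVs, or say that 13 is the analysed subset and how it was chosen.
3. State the number of carriers and of siblings expected to have follow-up data, as distinct from families contacted.
4. Restate power, or the variance detectable at 80% power, over a labelled retention range. On 500 and 150, the entries for detectable variance would be 2.0% (siblings), 5.1% or 5.5% (13 or 16 CNVs) and 3.2% (PRS) at 90%; and 2.2%, 5.7% or 6.2%, and 3.6% at 80%. If the reconciled starting counts differ, recompute from those.

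The cost is revised text and a short recalculation. No extra recruitment and no change to assessments or analyses is needed.

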## **7 Data Management**

### **7.1 Source Documents**

Source documents are original documents, data, and records from which participants' CRF data are obtained. These include, but are not limited to, hospital records (from which medical history and previous and concurrent medication may be summarised into the CRF), clinical and office charts, laboratory and pharmacy records, diaries, microfiches, radiographs, and correspondence. All documents will be stored safely in confidential conditions. On all study-specific documents, other than the signed consent, the participant will be referred to by the study participant number/code, not by name.

### **7.2 Direct Access to source data / documents**

Only members of the study research team and authorised representatives from the sponsor will have direct access to the source data and study documentation. All source data and study documentation will also be available to external auditors if and when required, and inspectors in the event of regulatory inspection. Access to the final data set will remain with the chief investigator.

### **7.3 Data Recording and Record Keeping**

Identifiable information will be stored in the Data Safe Haven and linked to a unique study ID (allocated as part of IMAGINE-1). Data will be collected with questionnaires created on Redcap and linked to a secure database on the UCL Data Safe Haven ([DSH](#)). The participants will be identified by a unique study specific number in any database. The name and any other identifying detail will NOT be included in any study data electronic file. [The NPD data will be accessed through the Office for National Statistics Secure Research Service \(ONS SRS\). The HES data will be processed and stored on the UCL DSH, and will be flowed onto ONS SRS for analysis with the NPD according to the](#)

[agreements with the DfE and NHS Digital](#). Anonymised data will be kept after the study has ended and made accessible to *bona fide* and authorised medical researchers.

Paper documents will be stored securely and only accessible by study staff and authorised personnel. Samples will be stored in a secure manner and in accordance with the Data Protection Act 1998, GDPR and HTA. We may send anonymized data collected as part of the study (e.g. questionnaire responses, genetics, interview recording, biological samples) outside the European Economic Area (EEA). The information will only be used by organisation and researchers to conduct research in accordance with the UK Policy Framework for Health and Social Care Research. The participant information could be used for research in any aspect of health or care and could be combined with information about the participant from other sources held by researchers (in the UK or abroad), the NHS or government.

### 7.3.1 Archiving

Archiving will be authorised by the Sponsor following submission of the end of study report. Essential documents will be retained for a **minimum** of 20 years after completion of the study in line with the [UCL data retention schedule](#) and MRC research practice principles and guidelines ([MRC GRP B.3](#)).

## 8 Patient Confidentiality & Data Protection

The participants will be identified only by initials and a participant ID number on the CRF and any electronic database. All documents will be stored securely and only accessible by study staff and authorised personnel. The study will comply with the Data Protection Act, which requires data to be anonymised as soon as it is practical to do so.

**Contacting participants using video-conferencing software:** We will use Microsoft Teams (UCL and Cardiff) and Zoom enterprise (Cardiff) with participants that wish to be contacted using video-conferencing software.

**Microsoft Teams:** To ensure that confidentiality is maintained, participants will be advised that it is their responsibility to ensure they have adequate anti-virus protection on their computers. They will be made aware that the video-conferencing sessions are recorded and stored in the Local University researcher's Team account. They will be advised that only members of the research team and auditors from Microsoft will have access to these recordings. They will also be made aware that some personal information from their Microsoft Teams account is stored locally on the computer (this is particularly important if participants intend to use public or shared computers). They will also be advised to logout of their Microsoft Teams account when not in use.

**Zoom:** Cardiff University holds an 'Enterprise' account with Zoom, thus interviews conducted by Zoom will be protected by Cardiff University data securities. However, In order to ensure the security of the online meeting when we set up the meetings we will:

- Password protect the meeting
- Meeting ID will be randomly generated
- Disable 'join before host' and enable 'waiting room'
- Once the participant is on the call the meeting will be 'locked' to prevent unauthorised access
- Disable 'screen sharing'

To ensure that confidentiality is maintained, participants will be advised that the platforms calls are encrypted, but it is their responsibility to ensure they have adequate anti-virus protection on their computers. They will be made aware that some personal information from their Zoom account is stored locally on the computer (this is particularly important if participants intend to use public or shared computers). They will also be advised to logout of their Microsoft Zoom account when not in use.

The meeting will be recorded and saved locally on password-protect files on Cardiff University servers. This will allow the researchers at Cardiff to score the psychiatric symptoms and code the psychiatric diagnosis and also to discuss complicated symptoms in consensus meetings led by a Child and Adolescent Psychiatrists in order to achieve the best-suited diagnosis.

**Managing, storing and curating data:** Assessments in this cohort study will be online using commercial software and that software adheres to rigorous standards, both here and in the United States. There will be pseudonymization of all data, with codes to allow linkage to identifiable data which is kept securely and separately. Information necessary to administer recruitment to the study was kept on a designated secure computer network. IMAGINE patient data is held in CiviCRM, which is an open-source patient management software, and stored in AIMEs secure hosted environment licensed to University of Cambridge. This database will be transferred to the UCL Data Safe Haven at the outset of IMAGINE-2. Research data will be collated and stored in the UCL Data Safe Haven, transferred securely from the originating source (secure server for online assessment data or secure storage at University of Cardiff for offline testing). Data will be held in a MySQL database within the UCL Data Safe Haven, linked through unique identifiers. Institutional guidance on research data management will be used to ensure adherence to guidelines and best practice, and researchers will contribute to development of institutional strategy.

All documents will be stored securely and only accessible by study staff and authorised personnel. The study will comply with the Data Protection Act, which requires data to be anonymised as soon as it is practical to do so. Assessments in this cohort study will be online using commercial software and that software adheres to rigorous standards, both here and in the United States. There will be pseudonymization of all data, with codes to allow linkage to identifiable data which is kept securely and separately. Information necessary to administer recruitment to the study was kept on a designated secure computer network. Phenotypic Research data will be collated and stored in the MRC Centre for Neuropsychiatric Genetics & Genomics under the Data Protection Act protected in Cardiff University's secure environment. Biological samples will be stored in the laboratory in the University of Cardiff MRC Centre for Neuropsychiatric Genetics & Genomics in adherence with the Human Tissue Act.

**Formal information/data security standards:** Data collected using US servers will comply with US laws - the HITECH Act of 2009 and the Health Insurance Portability and Accountability Act (HIPAA) of 1996 and all subsequent amendments. Data at rest will be encrypted and site security addressed multiple times per day. In the UK, we will work to the principle that information governance is about providing legitimate access to these data whilst protecting information from unauthorized access, disclosure and loss. All database providers are aware of the need to identify and assess potential risks to the security of the information within the project and are developing appropriate procedures, policies and security systems. The work in this package will be guided by the appropriate sections of the NHS IG Toolkit, ISO27001, data protection legislation (GDPR/DPA 2018), the Information Commissioner Office recommendations and best practice in IT security technologies.

## Sample Collection, Storage, Transfer and Analysis

### Sample Collection

Sample collection will take place either in the participant's home, or in the clinic at the Hadyn Ellis Building at Cardiff University and then stored in the laboratory in the Hadyn Ellis Building (MRC Centre for Neuropsychiatric Genetics & Genomics).

### Biological sample analysis

The procedures undertaken on the biological samples will be: Whole Genome Sequencing (WGS), cell signalling proteomic analysis, and induced Pluripotent Stem Cell (iPSC) generation to create cell lines and brain organoids. These procedures will all be performed using blood samples. If a participant has provided a saliva sample, we use this to perform genetic analysis including clarifying the presence or absence (in family members of child with a CNV) of a CNV as well as WGS. However, saliva samples cannot be used to investigate cell signalling or for iPSC generation.

From the DNA collected we will conduct:

**Whole Genome Sequencing:** This will be performed using the Illumina HiSeqX (150 bp paired end) at coverage of >30X. Variant Call Files will be generated from BWA-MEM alignments using the GATK4 haplotype caller by the TCAG sequencing facility, using a structural variant (SV) calling pipeline. This short-read pipeline is a composite of 4 complementary methods for detection of deletions, duplications, balanced rearrangements and mobile element insertions (MEIs). Short and long tandem repeat (TR) variants will be typed using *hipSTR* and GangSTR respectively. We will ensure that all alignment and calling of WGS data for all subjects, existing and new, will be performed using the same methodology.

We recognize that each individual CNV has distinct effects and a characteristic spectrum of clinical outcomes, and factors that explain variability in clinical outcome may also differ between CNVs. We will define components of secondary genetic risk including rare coding and non-coding variants and PRS. We will investigate the contributions of secondary rare variants and common variation to clinical outcome/dimensions across four CNV alleles at two loci.

**ERK Pathway Analysis:** We aim to collect blood samples from these individuals in order to screen for peripheral alterations in signalling components, including, among others, those belonging the ERK and the mTOR pathways. By conducting the same analysis in participating siblings of these individuals, we will be able to establish the degree to which these CNVs affect cell signalling, where we expect that those carrying the deletion will have higher overall ERK activity in the brain than controls, whereas those with the duplication will have lower overall levels than controls. This data will then be linked to the relevant phenotypic information we will collect (neurodevelopmental, psychiatric and cognitive function). Specifically, we aim to demonstrate that MAPK3/ERK1 genetic alterations in individuals with specific CNVs for which these pathways are implicated (e.g., those with 16p11.2 deletion or duplication or 22q11.2 deletion or duplication) are reflected in corresponding biochemical changes in blood samples, thus validating peripheral cell signalling changes as potential biomarkers

**Cell Signalling Analysis:** This will be performed on the same subset of individuals with CNV which can affect the ERK pathway to demonstrate in humans that genetic alterations in these CNVs are reflected in corresponding biochemical changes, as we have already found to be the case in mouse models. These analyses will be led by [name], who is an international expert on cell signalling pathways and take place in the laboratory of the Neuroscience and Mental Health Research Institute (NMHRI) / School of Biosciences at Cardiff University.

**Induced Pluripotent Stem (iPS) Cells:** Induced pluripotent stem cells (iPSCs) will be used to better understand how CNV lead to neuronal and glial alterations at the cellular level. We will generate factor-free iPS cell colonies that are more applicable to the establishment of human disease models and screening for biomarkers. We will derive neural stem cells from Peripheral Blood Mononuclear Cells (PBMCs) which will be extracted from a participant's blood sample. The PBMCs will be reprogrammed using the Cytotune-iPS 2.0 reprogramming kit. This process can take between 9 and 28 days to complete and at the end of this process live staining highlights undifferentiated iPSCs; the healthiest undifferentiated iPSCs are moved to a fresh culture dish for passage. We will characterize and define the neural phenotype associated with the disorder related cells and compare these to normal neurons and glial cells using a variety of techniques including receptor and cell surface antibodies, immunocytochemistry, morphology, functional analysis and electrophysiology. The generation of iPSCs will be led by [name], who is an international expert on iPSCs and take place in the laboratory of the Neuroscience and Mental Health Research Institute (NMHRI) / School of Biosciences in at Cardiff University.

**Brain organoids:** Cerebral organoid or Brain organoids represent a new model system for deciphering mechanisms of human brain development at a considerable level of detail outside the human body. They provide the relevant human background and the complex 3D arrangement of cells in a tissue context. As technology can bridge the gap between non-human animal models and reductionist human two-dimensional monolayer cell culture techniques, it is becoming model of choice for drug discovery. The method for the generation of homogeneous and reproducible organoids from induced pluripotent stem cells (iPSC) involves:

- 1) the generation of embryoid bodies from iPSC,
- 2) The induction of anterior cortical neuroectoderm,
- 3) the embedding of neuroectodermal aggregates in a matrix scaffold (Matrigel),
- 4) the generation of forebrain-type organoids from neuroectodermal aggregates; and
- 5) the fixation and validation of forebrain-type organoids.

Further, the organoids protocol can be further optimized to derive more oligodendrocytes or microglia to study effect of myelin or inflammation on brain development. Following generation of the organoids, the organoids will be assessed for their size, maturity, cellular heterogeneity and cortical layer formation. The two big limitations of the current protocol are

- 1) organoids lack externally recognizable body axes that guide their gross morphogenesis that can aid the phenotypic analysis,
- 2) Heterogeneity among the organoids from different batches.

**Keratinocyte-iPS Analysis:** Keratinocytes will be cultured using a defined, serum-free, feeder-independent medium; from this culture iPS cells will be generated using a non-viral reprogramming method. This will involve transfection of a transposon-based vector call piggyBac encoding the five reprogramming factors (c-Myc, Klf4, Oct4, Sox2 and Lin28). The vector can be removed once reprogramming has been achieved without leaving 'footprint mutations.' This method therefore allows for the generation of factor-free iPS cell colonies that are more applicable to the establishment of human disease models and screening for biomarkers and drug targets. The iPS cell colonies will then be selected on their morphologic appearance, their expression markers of pluripotency, and the capacity for generate all three germ-cell types. To confirm that the generated iPS cell lines are genetically matched to their parental somatic lines, and to rule out the possibility of cross contamination from existing cultures, PCR and DNA fingerprint analysis will be used. We expect to successfully generate iPS cells from each participant and derive neural stem cells from these iPS lines; we also expect to successfully derive neurons with an identical genotype. We will characterize and define the neural phenotype associated with the disorder related cells and compare these to

normal neurons using a variety of techniques including receptor and cell surface anti-bodies, immunocytochemistry, morphological analysis and electrophysiology.

